6.14. Sample Disposition and Storage (Non-PK Samples)

Samples will be processed and retained according to local practice and the regulations pertaining to each institution. No samples will be obtained or retained by Gilead.

CCI

[REDACTED]

[REDACTED]

7. ADVERSE EVENTS AND TOXICITY MANAGEMENT

7.1. Definitions of Adverse Events and Serious Adverse Events

7.1.1. Adverse Events

An AE is any untoward medical occurrence in a clinical study subject administered an investigational product, which does not necessarily have a causal relationship with the treatment. An AE can therefore be any unfavorable and/or unintended sign, symptom, or disease temporally associated with the use of an investigational product, whether or not considered related to the investigational product. AEs may also include pretreatment or posttreatment complications that occur as a result of protocol specified procedures or special situations (Section 7.6).

An AE does not include the following:

- Medical or surgical procedures such as surgery, endoscopy, tooth extraction, and transfusion. The condition that led to the procedure may be an AE and must be reported.
- Preexisting diseases, conditions, or laboratory abnormalities present or detected before the screening visit that do not worsen
- Situations where an untoward medical occurrence has not occurred (eg, hospitalization for elective surgery, social and/or convenience admissions)
- Overdose without clinical sequelae (Section 7.6.1)
- Any medical condition or clinically significant laboratory abnormality with an onset date before the consent form is signed and not related to a protocol-associated procedure is not an AE. It is considered to be preexisting and should be documented as medical history.

Preexisting events or conditions that increase in severity or change in nature after the consent form is signed or as a consequence of participation in the clinical study will be considered AEs

7.1.2. Serious Adverse Events

A SAE is defined as an event that, at any dose, results in the following:

- Death
- Life-threatening (Note: The term “life-threatening” in the definition of “serious” refers to an event in which the subject was at risk of death at the time of the event; it does not refer to an event that hypothetically might have caused death if it were more severe.)
- In-patient hospitalization or prolongation of existing hospitalization
- Persistent or significant disability/incapacity
- A congenital anomaly/birth defect

- A medically important event or reaction: such events may not be immediately life-threatening or result in death or hospitalization but may jeopardize the subject or may require intervention to prevent one of the other outcomes constituting SAEs. Medical and scientific judgment must be exercised to determine whether such an event is a reportable under expedited reporting rules. Examples of medically important events include intensive treatment in an emergency room or at home for allergic bronchospasm; blood dyscrasias or convulsions that do not result in hospitalization; and development of drug dependency or drug abuse.

7.2. Assessment of Adverse Events and Serious Adverse Events

The investigator or qualified subinvestigator is responsible for assessing AEs and SAEs for causality and severity, and for final review and confirmation of accuracy of event information and assessments.

7.2.1. Assessment of Causality for Study Drugs and Procedures

The investigator or qualified subinvestigator is responsible for assessing the relationship to study drug using clinical judgment and the following considerations:

- **No:** Evidence exists that the AE has an etiology other than the study drug. For SAEs, an alternative causality must be provided (eg, preexisting condition, underlying disease, intercurrent illness, or concomitant medication).
- **Yes:** There is reasonable possibility that the AE may have been caused by the study drug.

It should be emphasized that ineffective treatment should not be considered as causally related in the context of AE reporting.

The relationship to study procedures (eg, invasive procedures such as venipuncture or biopsy) should be assessed using the following considerations:

- **No:** Evidence exists that the AE has an etiology other than the study procedure.
- **Yes:** The AE occurred as a result of protocol procedures (eg, venipuncture)

7.2.2. Assessment of Severity

The severity of AEs will be graded using the Division of AIDS (DAIDS) Table for Grading the Severity of Adult and Pediatric Adverse Events, Version 2.1 dated July 2017. For each episode, the highest grade attained should be reported as defined in the grading scale. The DAIDS scale is available at the following location:

<https://rsc.niaid.nih.gov/sites/default/files/daidsgradingcorrectedv21.pdf>

7.3. Investigator Requirements and Instructions for Reporting Adverse Events and Serious Adverse Events

7.3.1. Requirements for Collection Prior to Study Drug Initiation

After informed consent, but prior to initiation of study medication, the following types of events must be reported on the applicable eCRFs: all SAEs and AE related to protocol-mandated procedures.

7.3.2. Adverse Events

Following initiation of study medication, collect all AEs, regardless of cause or relationship, throughout the duration of the study, including the protocol-required post treatment follow-up period must be reported on the eCRFs as instructed.

All AEs and clinically significant laboratory abnormalities should be followed up until resolution or stability of the abnormality has been demonstrated, if possible. Gilead may request that certain AEs be followed beyond the protocol-defined follow-up period.

7.3.3. Serious Adverse Events

All SAEs, regardless of cause or relationship, that occurs after the subject first consents to participate in the study (ie, signing the informed consent) and throughout the duration of the study, including the protocol-required post treatment follow-up period must be reported on the applicable eCRFs and Pharmacovigilance an Epidemiology (PVE) as instructed below in this section. This also includes any SAEs resulting from protocol-associated procedures performed after informed consent is signed.

Any SAEs and deaths that occur after the post-treatment follow-up visit but within 30-days of the last dose of study drug, regardless of causality, should also be reported.

Investigators are not obligated to actively seek SAEs after the protocol-defined follow-up period; however, if the investigator learns of any SAEs that occur after the protocol-defined follow-up period has concluded and the event is deemed relevant to the use of study drug, the investigator should promptly document and report the event to Gilead PVE.

All AEs and SAEs will be recorded in the eCRF database within the timelines outlined in the eCRF completion guidelines.

7.3.3.1. Electronic Serious Adverse Event (eSAE) Reporting Process

- Site personnel record all SAE data on the applicable eCRFs and from there transmit the SAE information to Gilead PVE within 24 hours of the investigator's knowledge of the event. Detailed instructions can be found in the eCRF completion guidelines.

- If it is not possible to record and submit the SAE information electronically, because the eCRF database cannot be accessed or is not available (including at study-start), record the SAE on the paper SAE reporting form and submit within 24 hours to:

Gilead PVE

Email: PPD

or

Fax: PPD

- As soon as it is possible to do so, any SAE reported via paper must be transcribed on the applicable eCRFs according to instructions and within the timelines outlined in the eCRF completion guidelines.
- If an SAE has been reported via a paper form because the eCRF database has been locked, no further action is necessary.
- For fatal or life-threatening events, copies of hospital case reports, autopsy reports, and other documents are also to be submitted by email or fax when requested and applicable. Transmission of such documents should occur without personal subject identification, maintaining the traceability of a document to the subject identifiers.
- Additional information may be requested to ensure the timely completion of accurate safety reports.
- Any medications necessary for treatment of the SAE must be recorded onto the concomitant medication section of the subject's eCRF and the SAE narrative section of the Safety Report Form eCRF.

7.4. Gilead Reporting Requirements

Depending on relevant local legislation or regulations, including the applicable US FDA Code of Federal Regulations, the European Union (EU) Clinical Trials Directive (2001/20/EC) and relevant updates, and other country-specific legislation or regulations, Gilead may be required to expedite to worldwide regulatory agencies reports of SAEs, serious adverse drug reactions (SADRs), or suspected unexpected serious adverse reactions (SUSARs). In accordance with the EU Clinical Trials Directive (2001/20/EC), Gilead or a specified designee will notify worldwide regulatory agencies and the relevant IEC in concerned Member States of applicable SUSARs as outlined in current regulations.

Assessment of expectedness for SAEs will be determined by Gilead using reference safety information specified in the investigator's brochure or relevant local label as applicable.

All investigators will receive a safety letter notifying them of relevant SUSAR reports associated with any study drug. The investigator should notify the IRB or IEC of SUSAR reports as soon as is practical, where this is required by local regulatory agencies, and in accordance with the local institutional policy.

7.5. Clinical Laboratory Abnormalities and Other Abnormal Assessments as Adverse Events or Serious Adverse Events

Laboratory abnormalities without clinical significance are not recorded as AEs or SAEs. However, laboratory abnormalities (eg, clinical chemistry, hematology, and urinalysis) that require medical or surgical intervention or lead to study drug interruption, modification, or discontinuation must be recorded as an AE, as well as an SAE, if applicable. In addition, laboratory or other abnormal assessments (eg, electrocardiogram, x-rays, vital signs) that are associated with signs and/or symptoms must be recorded as an AE or SAE if they meet the definition of an AE or SAE as described in Sections 7.1.1 and 7.1.2. If the laboratory abnormality is part of a syndrome, record the syndrome or diagnosis (eg, anemia), not the laboratory result (ie, decreased hemoglobin).

Laboratory abnormalities that do not require medical intervention or action are generally not considered AEs.

Severity should be recorded and graded according to the DAIDS Table for Grading the Severity of Adult and Pediatric Adverse Events, Version 2.1 dated July 2017. For AEs associated with laboratory abnormalities, the event should be graded on the basis of the clinical severity in the context of the underlying conditions; this may or may not be in agreement with the grading of the laboratory abnormality.

7.6. Special Situations Reports

7.6.1. Definitions of Special Situations

Special situation reports include all reports of medication error, abuse, misuse, overdose, occupational exposure, drug interactions, exposure via breastfeeding, unexpected benefit, transmission of infectious agents via the product, counterfeit of falsified medicine, and pregnancy regardless of an associated AE.

Medication error is any unintentional error in the prescribing, dispensing, preparation for administration or administration of an investigational product while the medication is in the control of a health care professional, patient, or consumer. Medication errors may be classified as a medication error without an AE, which includes situations of missed dose; medication error with an AE; intercepted medication error; or potential medication error.

Abuse is defined as persistent or sporadic intentional excessive use of an investigational product by a subject.

Misuse is defined as any intentional and inappropriate use of an investigational product that is not in accordance with the protocol instructions or the local prescribing information.

An overdose is defined as an accidental or intentional administration of a quantity of an investigational product given per administration or cumulatively which is above the maximum recommended dose as per protocol or in the product labeling (as it applies to the daily dose of the subject in question). In cases of a discrepancy in drug accountability, overdose will be established only when it is clear that the subject has taken the excess dose(s). Overdose cannot be established when the subject cannot account for the discrepancy except in cases in which the investigator has reason to suspect that the subject has taken the additional dose(s).

Occupational exposure is defined as exposure to an investigational product as a result of one's professional or non-professional occupation.

Drug interaction is defined as any drug/drug, drug/food, or drug/device interaction.

Unexpected benefit is defined as an unintended therapeutic effect where the results are judged to be desirable and beneficial.

Transmission of infectious agents is defined as any suspected transmission of an infected agent through a Gilead investigational product.

Counterfeit or falsified medicine: Any investigational product with a false representation of:
a) its identity, b) its source, or c) its history.

7.6.2. Instructions for Reporting Special Situations

7.6.2.1. Instructions for Reporting Pregnancies

The investigator should report pregnancies in female study subjects that are identified after initiation of study drug and throughout the study, including the post study drug follow-up period, to the Gilead PVE using the pregnancy report form within 24 hours of becoming aware of the pregnancy.

Gilead PVE

Email: PPD

or

Fax: PPD

Refer to Section 7.3 and the eCRF completion guidelines for full instructions on the mechanism of pregnancy reporting.

The pregnancy itself is not considered an AE nor is an induced elective abortion to terminate a pregnancy without medical reasons.

Any premature termination of pregnancy (eg, a spontaneous abortion, an induced therapeutic abortion due to complications or other medical reasons) must be reported within 24 hours as an SAE. The underlying medical reason for this procedure should be recorded as the AE term.

A spontaneous abortion is always considered to be an SAE and will be reported as described in Sections 7.3.3. Furthermore, any SAE occurring as an adverse pregnancy outcome post study must be reported to Gilead PVE.

The subject should receive appropriate monitoring and care until the conclusion of the pregnancy. The outcome should be reported to Gilead PVE using the pregnancy outcome report form. If the end of the pregnancy occurs after the study has been completed, the outcome should be reported directly to Gilead PVE. Gilead PVE contact information is as follows:

email: PPD and fax: PPD

Pregnancies of female partners of male study subjects exposed to Gilead or other study drugs must also be reported and relevant information should be submitted to Gilead PVE using the pregnancy and pregnancy outcome forms within 24 hours. If the end of the pregnancy occurs after the study has been completed, the outcome should be reported directly to Gilead PVE, fax number PPD or email PPD

Refer to [Appendix 3](#) for Pregnancy Precautions, Definition for Female of Childbearing Potential, and Contraceptive Requirements.

7.6.2.2. Reporting Other Special Situations

All other special situation reports must be reported on the special situations report form and forwarded to the Gilead PVE within 24 hours of the investigator becoming aware of the situation. These reports must consist of situations that involve study drug and/or Gilead concomitant medications, but do not apply to non-Gilead concomitant medications.

Gilead PVE

Email: PPD

or

Fax: PPD

Special situations involving non-Gilead concomitant medications do not need to be reported on the special situations report form; however, special situations that result in AEs due to a non-Gilead concomitant medication, must be reported as an AE.

Any inappropriate use of concomitant medications prohibited by this protocol should not be reported as “misuse,” but may be more appropriately documented as a protocol deviation.

Refer to Section 7.3 and the eCRF completion guidelines for instructions on special situation reporting.

All clinical sequelae in relation to these special situation reports will be reported as AEs or SAEs at the same time using the AE eCRF and/or the SAE report form. Details of the symptoms and signs, clinical management, and outcome will be reported, when available.

8.2. Planned Analyses

8.2.1. Interim Analysis

Prior to the final analysis, the primary analysis of the primary endpoint will be conducted, additional interim analyses may be conducted, and the analyses may be submitted to regulatory agencies to seek guidance for the overall clinical development program or for other purposes.

8.2.1.1. DMC Analysis

The DMC will review safety and efficacy data on a regular basis.

8.2.2. Primary Analysis

The primary analysis will be performed after all participants have completed 14 days in Part A of the study or prematurely terminated from Part A of the study prior to 14 days.

8.2.3. Final Analysis

The final analysis will be performed after all participants have completed the study or prematurely terminated from the study, outstanding data queries have been resolved or adjudicated as unresolvable, and the data have been cleaned and finalized.

8.3. Analysis Conventions

8.3.1. Analysis Sets

8.3.1.1. Efficacy

The primary analysis set for efficacy analysis is defined as the full analysis set (FAS), which will include all participants who (1) are randomized into Part A of the study and (2) have received at least 1 dose of RDV. Participants will be grouped according to the treatment to which they were randomized.

8.3.1.2. Safety

The primary analysis set for safety analyses is defined as the Safety Analysis Set, which will include all participants who (1) are randomized into the study and (2) have received at least 1 dose of RDV. Participants will be grouped according to the treatment to which they were randomized for Part A (5-day dosing group or 10-day dosing group) and according to the treatment to which they were assigned for Part B (Mechanically Ventilated Treatment Group or Extension Treatment Group).

8.3.1.3. Expanded RDV-Treated Analysis Set

The Expanded RDV-Treated Analysis Set will include participants who have received at least 1 dose of RDV in either the Mechanically Ventilated Treatment Group or Extension Treatment Group. This analysis set will be used for both the safety and efficacy evaluations for participants enrolled in Part B.

8.3.2. Data Handling Conventions

CCI

Laboratory data that are continuous in nature but are less than the lower limit of quantitation or above the upper limit of quantitation, will be imputed to the value of the lower or upper limit plus or minus 1 significant digit, respectively (eg, if the result of a continuous laboratory test is < 20, a value of 19 will be assigned).

Missing data can have an impact upon the interpretation of the trial data. In general, values for missing data will not be imputed. However, a missing pre-treatment laboratory result would be treated as normal (ie, no toxicity grade) for the laboratory abnormality summary.

All available data for participants that do not complete the study will be included in data listings

8.4. Demographic and Baseline Characteristics Analysis

Demographic and baseline measurements will be summarized using standard descriptive methods. Demographic summaries will include sex, race/ethnicity, and age. For categorical demographic and baseline characteristics, a Cochran Mantel Haenszel test will be used to compare treatment groups in Part A. For continuous demographic and baseline characteristics, a Wilcoxon rank sum test will be used to compare treatment groups in Part A.

8.5. Efficacy Analysis

8.5.1. Primary Analysis

The primary endpoint will be analyzed using a proportional odds model. The null hypothesis being tested is whether the odds of improvement on the ordinal scale is the same for the two treatment groups (ie, whether the common odds ratio is equal to 1). The odds ratio and 95% confidence interval will be provided.

The proportion of subjects in each category will be summarized by treatment group. The validity of the proportionality assumption will be evaluated.

If a participant is discharged prior to Day 14, the Day 14 ordinal scale category is considered to be not hospitalized. Every effort will be made to obtain clinical status data for all subjects prior to discharge. Subjects who have missing clinical status information on Day 14 will be excluded from the primary analysis.

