3.2. Study Design

Part A of this study is a randomized, open-label, multicenter study of RDV in participants with severe COVID-19 infection. Eligible participants will be randomized in equal proportions to 1 of 2 treatment groups. No stratification will be performed. Part B is a two treatment group multicenter study of RDV in participants with severe COVID-19 infection.

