3.3. Study Treatments

In Part A, approximately 400 participants who meet all eligibility criteria and who are not mechanically ventilated may be randomized in a 1:1 ratio into 1 of the following treatment groups:

Treatment Group 1: continued standard of care therapy together with IV RDV 200 mg on Day 1 followed by IV RDV 100 mg on Days 2, 3, 4, and 5

Treatment Group 2: continued standard of care therapy together with IV RDV 200 mg on Day 1 followed by IV RDV 100 mg on Days 2, 3, 4, 5, 6, 7, 8, 9, and 10

In Part B, an additional approximately 5600 participants who meet all of the eligibility criteria may receive:

Mechanically Ventilated Treatment Group: continued standard of care therapy together with IV RDV 200 mg on Day 1 followed by IV RDV 100 mg on Days 2, 3, 4, 5, 6, 7, 8, 9, and 10

Extension Treatment Group: continued standard of care therapy together with IV RDV 200 mg on Day 1 followed by IV RDV 100 mg on Days 2, 3, 4, 5, 6, 7, 8, 9, and 10 unless the 5-day dosing regimen used in Treatment Group 1 of Part A is selected. If treatment for 5 days is selected, all participants in the Extension Treatment Group and all new participants will be reassigned to receive treatment for a total of 5 days. National and local regulatory authorities will be informed.

Participants in Part A of the study will be the primary efficacy population. Participants enrolled in Part B will have data reported descriptively at study completion.

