4.2. Inclusion Criteria

Subjects must meet all of the following inclusion criteria to be eligible for participation in this study:

- 1) Willing and able to provide written informed consent, or with a legal representative who can provide informed consent, or enrolled under ICH E6(R2) 4.8.15 emergency use provisions as deemed necessary by the investigator (participants ≥ 18 years of age), or willing and able to provide assent (participants ≥ 12 and < 18 years of age, where locally and nationally approved) prior to performing study procedures. For participants ≥ 12 and < 18 years of age, a parent or legal guardian willing and able to provide written informed consent prior to performing study procedures
- 2) Aged ≥ 18 years (at all sites), or aged ≥ 12 and < 18 years of age weighing ≥ 40 kg (where permitted according to local law and approved nationally and by the relevant institutional review board [IRB] or independent ethics committee [IEC])
- 3) SARS-CoV-2 infection confirmed by PCR test ≤ 4 days before randomization
- 4) Currently hospitalized
- 5) $SpO_2 \leq 94\%$ on room air or requiring supplemental oxygen at screening
- 6) Radiographic evidence of pulmonary infiltrates
- 7) Men and women of childbearing potential who engage in heterosexual intercourse must agree to use protocol specified method(s) of contraception as described in [Appendix 3](#).

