5. INVESTIGATIONAL MEDICINAL PRODUCTS

5.1. Randomization, Blinding, and Treatment Codes Access

5.1.1. Randomization

Subjects who meet eligibility criteria will be randomized in a 1:1 ratio to 1 of 2 treatment groups on Day 1 using an IWRS and assigned a subject number. Randomization will not be stratified.

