6.2. Pretreatment Assessments

6.2.1. Screening Visit

Subjects will be screened within 2 days before randomization and dosing to determine eligibility for participation in the study.

- Obtain written informed consent, or with a legal representative who can provide informed consent, or enrolled under ICH E6(R2) 4.8.15 emergency use provisions as deemed necessary by the investigator (participants ≥ 18 years of age), or obtain assent (participants age ≥ 12 to < 18 , where locally and nationally approved)

After the informed consent the following assessments are performed to determine eligibility requirements as specified in the inclusion and exclusion criteria:

- Focused medical history including the following information (eg, date of first symptoms, overall symptoms, exposure source, demographics, baseline characteristics), allergies and medical history
- Review and record medications and therapies for this current illness
- Counsel subjects to use adequate birth control methods required during the trial to avoid pregnancy
- Targeted physical examination including, vital signs (heart rate, temperature, blood pressure), body weight, and height
- Documentation of respiratory status:

Respiratory Rate

- Oxygen supplementation: room air, low flow O₂ (L/min and %), high flow O₂ (L/min and %), CPAP/BIPAP (FiO₂ or %), mechanical ventilation (FiO₂ or %), ECMO

Oxygenation: SpO₂ or PaO₂

Radiographic findings

- Obtain blood samples if not done in the preceding 48 hours for creatinine, creatinine clearance, ALT and AST
- Pregnancy test (for women of childbearing potential)
- Record any SAEs and all AEs related to protocol-mandated procedures occurring after signing of the consent (or assent) form.

Study subjects who qualify should be immediately randomized. Randomization and dosing should occur on the same day if possible.

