6.2.2. Baseline/Day 1 Assessments

The following evaluations are to be completed at the Day 1 visit. The investigator must have confirmed eligibility before proceeding with randomization (Part A) or treatment assignment (Part B) on the Day 1 visit. If the screening and Day 1 visits occur within one day, no procedures need to be repeated. Participants must complete the following assessments before being administered study drug:

- Physical examination including vital signs (heart rate, temperature, blood pressure, and body weight)
- Documentation of respiratory status:

Respiratory rate

Oxygen supplementation: room air, low flow O₂ (L/min and %), high flow O₂ (L/min and %), CPAP/BIPAP (FiO₂ or %), mechanical ventilation (FiO₂ or %), ECMO

Oxygenation: SpO₂ or PaO₂

Radiographic findings (if available)

- Review AEs and document concomitant medications
- Obtain blood samples for white blood cell count, hemoglobin and/or hematocrit, platelets, creatinine and creatinine clearance, glucose, total bilirubin, ALT, AST

█

- Review the Ordinal Scale (see Section 6.9)

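### Protocol 8.5.1 names no baseline covariate for the Part A primary model, although a pre-dose score on the endpoint's own scale is collected: an optional gain in power, not an error

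*Protocol*

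**What the plan says.** Protocol Section 8.5.1 gives the Part A primary analysis as follows: "The primary endpoint will be analyzed using a proportional odds model". The null hypothesis is a common odds ratio of 1 between the two groups. No covariate is listed there or in the synopsis.

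The design does not balance baseline severity. Section 5.1.1 states "Randomization will not be stratified", and Section 3.2 states "No stratification will be performed".

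Part A takes eligible participants "who are not mechanically ventilated may be randomized in a 1:1 ratio" (Section 3.3). Under Section 4.2 they have low oxygen saturation "on room air or requiring supplemental oxygen at screening". Scores 3, 4 and 5 can therefore all occur at entry.

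Section 6.2.2 introduces the Day 1 list with "Participants must complete the following assessments before being administered study drug", and that list includes the ordinal scale. SAP Section 3.8.2 also describes an ordinal result recorded before dosing on Study Day 1.

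The supplied SAP covers Part B. Its Section 6.1 leaves the primary endpoint out, and its statement in Section 3.3 that no covariates are planned concerns Part B only.

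**The concern.** Baseline respiratory support may well predict Day 14 status on the same scale. If it does, an unadjusted proportional odds model leaves explainable variation in the outcome, and an adjusted model has more power with the same 400 participants. If it does not, adjustment gains nothing and costs almost nothing.

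The stake is efficiency, not validity. One practical condition applies. Section 8.3.2 generally does not impute missing values, so an adjusted model without a rule for a missing baseline score would drop participants and could lose what it gains.

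**Working it through.** **1. The plan's own figure.** Inputs from Protocol Section 8.9: N = 400 allocated 1:1, two-sided alpha 0.05, odds ratio 1.75, and Group 1 Day 14 distribution 2/4/7/13/16/20/38% for categories 1 to 7.

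- Applying the odds ratio at every cut gives Group 2: 1.15/2.37/4.35/8.85/12.55/18.98/51.75%.
- The averages over the two groups are 1.58/3.18/5.67/10.93/14.27/19.49/44.88%, so 1 − Σp³ = 0.8978.
- Power = Φ(ln 1.75 × √(400 × 0.8978 / 12) − 1.96) = Φ(0.5596 × 5.470 − 1.96) = Φ(1.101) = 86.5%.

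The stated figure of more than 85% is confirmed. It uses no covariate.

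**2. Power with baseline adjustment.** The documents give neither the baseline split over scores 3/4/5 nor its prognostic strength, so both are assumptions shown as ranges. Two splits were used, 25/55/20% and 10/75/15%. The baseline effect runs from 0 to 1.5 log-odds per score step; 0.5, 1.0 and 1.5 are odds ratios of about 1.6, 2.7 and 4.5.

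Cutpoints were calibrated so that Group 1 keeps the planning distribution, and the conditional odds ratio so that the unadjusted odds ratio stays at 1.75. Proportional odds models were fitted to expected counts with and without a three-level baseline factor, and power = Φ(β/SE − 1.96).

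Example, 25/55/20% at 1.0 per step: z = 3.031 unadjusted, giving Φ(1.071) = 85.8%; z = 3.243 adjusted, giving Φ(1.283) = 90.0%.

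| Log-odds per step | Unadjusted | Adjusted, 25/55/20 | Adjusted, 10/75/15 |
|---|---|---|---|
| 0 | 85.8% | 85.8% | 85.8% |
| 0.5 | 85.8% | 87.0% | 86.5% |
| 0.75 | 85.8% | 88.4% | 87.2% |
| 1.0 | 85.8% | 90.0% | 88.2% |
| 1.5 | 85.8% | 93.5% | 90.4% |

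The adjusted odds ratio is 1.76 to 1.95 across the non-zero rows.

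A separate simulation (2,000 trials per scenario, 25/55/20% split, Monte Carlo error about 0.8 points for power) points the same way. Adjustment added about 0 to 4 points for odds ratios of 1 to 3 per category. Type I error, checked at an odds ratio of 3, was 4.9% unadjusted and 5.0% adjusted.

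**3. Loss from missing baseline scores.** If participants without a score were dropped, the gain is cancelled at a missing share of 1 − (z unadjusted / z adjusted)². For the example: 1 − (3.031/3.243)² = 12.6%.

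| Log-odds per step | 25/55/20 | 10/75/15 |
|---|---|---|
| 0.5 | 3.6% (about 14 of 400) | 2.0% (about 8) |
| 0.75 | 7.6% | 4.3% |
| 1.0 | 12.6% (about 51) | 7.2% (about 29) |
| 1.5 | 24.0% | 13.9% |

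**4. Sparse baseline levels.** Trials were simulated with levels of fewer than 20 participants merged as set out in the fix.

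| Split (3/4/5) | Power at 0 per step, unadjusted to adjusted | Power at 1.0 per step, unadjusted to adjusted |
|---|---|---|
| 25/55/20 | 86.4 to 86.2% | 86.0 to 90.1% |
| 10/75/15 | 86.4 to 86.5% | 86.2 to 88.7% |
| 25/71/4 | 85.8 to 85.8% | 86.5 to 88.8% |
| 5/75/20 | 86.0 to 86.0% | 86.0 to 88.2% |

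Each power figure rests on 8,000 runs (SE 0.3 to 0.4 points). Merging acted in about 82% of runs for 25/71/4 and 47% for 5/75/20. Type I error (16,000 runs, SE 0.17 points) was 4.9 to 5.5% unadjusted and 4.7 to 5.5% adjusted, differing by at most 0.2 points within a scenario. The simulations in this step were run once; the fits in steps 2 and 3 were repeated and agree to within 0.1 point.

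**The case against.** The strongest reply is that the plan is internally consistent. There is no stratification factor to carry into the model, the sample size formula has no covariate term, and 8.5.1 is silent on covariates rather than excluding them. The Part A SAP may name one. SAP Sections 2.1.1 to 2.1.3 also report the Part A analyses as already performed, so the power gain may be out of reach. All of this stands. It is why the point is optional and why the fix starts with the Part A SAP.

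A second reply is that the baseline value is unsettled, because Protocol Section 6.9 records each day's worst score on the following day, so the Day 1 score could include time after dosing. SAP Section 3.8.2 answers this: it separates the pre-dose record from the daily worst scores that begin after the first dose.

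Three smaller objections stand in part:

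- The gain rests on assumed prognostic strength and on equal baseline steps with proportional odds. Departures from these were not tested.
- The threshold of 20 for merging is a convention.
- The missing-score rule does not help if oxygen support is also undocumented. Participants with missing Day 14 status remain excluded under 8.5.1 either way. Part of Section 8.3.2 is redacted, so a relevant rule may exist there.

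**Conclusion.** The point holds as an optional improvement, with moderate confidence. Section 8.5.1 lists no baseline covariate, although a pre-dose score on the endpoint's scale is collected. The unadjusted test is valid, and its power is as stated.

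Adjustment would add nothing if the baseline score is not prognostic, 0.7 to 4.2 points of power at 0.5 to 1.0 log-odds per step, and 4.6 to 7.7 points at 1.5. These figures depend on the assumed splits and effects, on proportional odds for both terms, and on a rule that keeps participants with a missing baseline score in the model. The gain applies to the primary test only if the model is fixed before Part A outcomes are reviewed.

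**What to change.** First check the Part A SAP. If it already names a baseline covariate, only bring the 8.5.1 text into line. Otherwise, if Part A outcomes have not been reviewed, add to 8.5.1:

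1. **Model.** Proportional odds with treatment and pre-dose ordinal score, the score as a categorical term.
2. **Baseline.** The pre-dose Day 1 value or, if that was not recorded, the last value before the first dose, as in SAP Section 3.8.2. The ordinal scale is not a screening assessment, so an earlier value may not exist. In that case assign the score from the oxygen support recorded before dosing (Protocol Sections 6.2.1, under "Documentation of respiratory status", and 6.2.2), reading the table in SAP Appendix 2 item 16 in reverse, with room air counted as 5.
3. **Sparse levels.** Starting from the lowest score, a level with fewer than 20 participants (5% of 400, arms pooled) joins the next lower level, or the next higher if it is the lowest. Repeat until no level is below 20.
4. **Reporting.** State that the adjusted odds ratio is conditional on baseline score, and report the unadjusted odds ratio as supportive.

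If Part A outcomes have been reviewed, as the SAP indicates, keep the primary analysis as specified and report the adjusted model as a labelled post hoc sensitivity analysis. It cannot then raise the power of the primary test.

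The cost is a short paragraph and no new assessment. The 1.75 in Section 8.9 would continue to refer to the unadjusted analysis, and the model adds a proportional odds assumption for the baseline term.
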